**8.7.1.5 Flow Chart**

| Event   | Screening   | Baseline  | Treatment period  |            |            |            |             |              |              |              |                  | FU visit  |
|---|---|-----------------------|-------------------------------|------------|------------|------------|-------------|--------------|--------------|--------------|------------------|-----------------------|
|   |   |                       | D8/
W1                     | D15/
W2 | D29/
W4 | D57/
W8 | D85/
W12 | D113/
W16 | D141/
W20 | D169/
W24 | EDV  |                       |
| Informed consent                                      | Written informed consent will be obtained before any study-related procedures and/or assessments are performed. |                       |                               |            |            |            |             |              |              |              |                  |                       |
| Inclusion/
exclusion criteria                      | X   | X         |                               |            |            |            |             |              |              |              |                  |                       |
| Demographic data and baseline disease characteristics | X   |                       |                               |            |            |            |             |              |              |              |                  |                       |
| Medical history/
concomitant illnesses             | X   |                       |                               |            |            |            |             |              |              |              |                  |                       |
| Physical examination                                  | X   | X                     |                               |            |            |            | X           |              |              | X            | X                | X                     |
| Serology                                  | X   |                       |                               |            |            |            |             |              |              |              |                  |                       |
| TB test and chest X-ray                   | X   |                       |                               |            |            |            |             |              |              |              |                  |                       |
| Pregnancy test                            | X   | X                     | X                             | X          | X          | X          | X           | X            | X            | X            | X                | X                     |
| 12-Lead ECG   | X   |                       |                               |            |            |            | X           |              |              | X            | X                | X                     |
| Vital signs                              | X   | X                     | X                             | X          | X          | X          | X           | X            | X            | X            | X                | X                     |
| Clinical laboratory tests                | X   | X                     | X                             | X          | X          | X          | X           | X            | X            | X            | X                | X                     |
| PK samples  blood                        |   |                       |                               |            | X          |            | X           |              |              | X            | X                |                       |
| PD samples  blood                        |   | X                     | X                             |            | X          |            | X           |              |              | X            | X                |                       |

 Subjects will begin to take their treatment on the next morning (Day 1) following randomization.

 During the treatment period, a visit time window of ± 2 calendar days is allowed.

 Follow-up visit will be performed only for subjects discontinuing prematurely from the study and for subjects not entering the Long Term Follow-up study GLPG0634-CL-205.

 Early discontinuation visit.

 Eligibility criteria check based on the laboratory results from the Screening visit.

 At Screening, includes height and weight.

 Includes Hepatitis B and C, HIV 1 and 2, RF, and anti-CCP.

 X-ray should be performed if results from an X-ray performed in the previous 3 months are not available at the site.

 For female subjects only. To be performed on serum at Screening and Week 24/EDV and on urine for other visits.

 Vital signs are defined as blood pressure (systolic and diastolic), HR, and oral temperature.

 Refer to Section 8.7.1.4.2.

 PK samples: 1 blood sample (2 mL) for analysis of GLPG0634 and its main metabolite (G254445) in plasma.

 PD samples: 4 blood samples (2x4 mL for serum preparation and 2x2.5 mL in PAXgene tubes) will be collected for analysis of serum (analytes and miRNA profiling) and whole blood (gene expression in circulating leukocytes, mRNA and miRNA profiling).

| Event   | Screening | Baseline  | Treatment period  |            |            |            |             |                 |              |              |                   | FU visit  |                                 |
|---|-----------|------------------------|--------------------------------|------------|------------|------------|-------------|-----------------|--------------|--------------|-------------------|------------------------|---------------------------------|
|   |           |                        | D8/
W1                      | D15/
W2 | D29/
W4 | D57/
W8 | D85/
W12 | D113/
W16    | D141/
W20 | D169/
W24 | EDV  |                        | W24 or
EDV +
7-10
days |
| Randomization                                 |           | X         |                                |            |            |            |             | X  |              |              |                   |                        |                                 |
| IXRS call                                     | X         | X                      | X                              | X          | X          | X          | X           | X               | X            | X            | X                 | X                      |                                 |
| Dispense study medication                     |           | X                      | X                              | X          | X          | X          | X           | X               | X            |              |                   |                        |                                 |
| Subject diary card dispensation  |           | X                      | X                              | X          | X          | X          | X           | X               | X            |              |                   |                        |                                 |
| Subject diary card collection                 |           |                        | X                              | X          | X          | X          | X           | X               | X            | X            | X                 |                        |                                 |
| Drug accountability check                     |           |                        | X                              | X          | X          | X          | X           | X               | X            | X            | X                 |                        |                                 |
| Study medication dosing                       |           |                        |                                |            |            |            |             |                 |              |              |                   |                        |                                 |
| Serum CRP                                     | X         | X                      | X                              | X          | X          | X          | X           | X               | X            | X            | X                 | X                      |                                 |
| SJC66   | X         | X                      | X                              | X          | X          | X          | X           | X               | X            | X            | X                 | X                      |                                 |
| TJC68   | X         | X                      | X                              | X          | X          | X          | X           | X               | X            | X            | X                 | X                      |                                 |
| Physician's Global Assessment                 |           | X                      | X                              | X          | X          | X          | X           | X               | X            | X            | X                 | X                      |                                 |
| Patient's Global Assessment                   | X         | X                      | X                              | X          | X          | X          | X           | X               | X            | X            | X                 | X                      |                                 |
| HAQ-DI  |           | X                      | X                              | X          | X          | X          | X           | X               | X            | X            | X                 | X                      |                                 |
| FACIT fatigue scale                           |           | X                      |                                |            | X          |            | X           |                 |              |              | X                 | X                      |                                 |
| SF-36 questionnaire                           |           | X                      |                                |            | X          |            | X           |                 |              |              | X                 | X                      |                                 |
| AE assessment                                 |           |                        |                                |            |            |            |             |                 |              |              |                   |                        |                                 |
| Concomitant medications                       |           |                        |                                |            |            |            |             |                 |              |              |                   |                        |                                 |

 Subjects will begin to take their treatment on the next morning (Day 1) following randomization.  
 During the treatment period, a visit time window of ± 2 calendar days is allowed.  
 Follow-up visit will be performed only for subjects discontinuing prematurely from the study and for subjects not entering the Long Term Follow-up study GLPG0634-CL-205.  
 Early discontinuation visit.  
 Upon qualification for the study.  
 At Week 12, subjects on placebo who have not achieved a 20% improvement in SJC66 and TJC68 will be re-randomized (automatically via IXRS) to treatment to receive GLPG0634 100 mg q.d. or 50 mg b.i.d. doses in a blinded fashion, subjects on 50 mg q.d. who have not achieved a 20% improvement in SJC66 and TJC68 will be assigned to 100 mg q.d. and subjects on 25 mg b.i.d. who have not achieved a 20% improvement in SJC66 and TJC68 will be assigned to 50 mg b.i.d. All will continue in the study until Week 24. Subjects in the other groups will maintain their randomized treatment until Week 24.  
 Subject diary card will be dispensed to subjects on D -1 and at every following visit; subjects should be instructed to bring their diary card along with them to all visits.

## **8.7.2 Appropriateness of Measurements**

The efficacy and safety assessments are widely used and generally recognized as reliable, accurate, and relevant to the disease condition.

## **8.8 Statistical Methods**

### **8.8.1 Statistical and Analytical Plans**

A detailed statistical analysis plan will be created and finalized prior to the interim database lock and final database lock.

#### **8.8.1.1 Datasets or Populations Analyzed**

All randomized subjects who received at least one dose of study medication and have at least one post-Baseline efficacy assessment will be included in the efficacy analysis (intent-to-treat [ITT]).

A secondary per-protocol analysis will be performed to confirm the ITT analysis, excluding subjects with major protocol deviations (such as Baseline CRP within normal range, Baseline TJC68 <8, Baseline SJC66 <6, <80% study medication compliance, or use of forbidden concomitant medications). Full details of the major protocol deviations will be described in the statistical analysis plan, with adherence to analysis sets agreed upon prior to database lock and unblinding.

All randomized subjects who received at least one dose of study medication will be included in the safety analysis.

All randomized subjects who received at least one dose of GLPG0634 and who have at least one PK measurement will be included in the PK analysis.

Reasons for study termination will be tabulated.

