#### 2.1.1. Efficacy data

Study period	Treatment groups	Analysis populations	Imputation method
“Chapter 2”: Periods 1+2 together (full 24 weeks period)	
The 7 original groups:
 
 
– Placebo
 
– GLPG0634 q.d. dosing groups:                             
 
• 50 mg q.d.
 
• 100 mg q.d.
 
• 200 mg q.d.
 
 
 
– GLPG0634 b.i.d. dosing groups:                             
 
• 25 mg b.i.d.
 
• 50 mg b.i.d.
 
• 100 mg b.i.d.
 
 
 
 
For the subjects in the placebo and low dose groups who switched to 100 mg/day during the second study period: they will be handled as if they discontinued at Week 12, and will be imputed from Week 12 onwards in the second study period.                      (Details: see further in the SAP)
	
ITT: all subjects randomized, exposed at least once, and with post-baseline data for at least one efficacy parameter.
 
Per-protocol: subpopulation of ITT, excluding all critical (=major) protocol deviations. This is decided during the blind review meeting before final database lock.
	
Observed case, non-responder imputation (NRI), last observation carried forward (LOCF): depending on the parameter; is specified later when all parameters are discussed.

Study period	Treatment groups	Analysis populations	Imputation method

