### **2.3.3. Per Protocol Population**

In case a particular subject would be unblinded (e.g., in case of an SAE), all efficacy data of this subject up to the point of unblinding will still qualify for the per-protocol efficacy analysis selection according to the above rule of excluding critical protocol deviations. Recorded efficacy data from the moment of unblinding onwards will be disqualified from the analysis. Such data will still be part of the listings, but will be labeled as use=no. Missing data after the moment of unblinding will be imputed using the same rules as used for other subjects.

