## 7.2. PROTOCOL DEVIATIONS AND ELIGIBILITY

Protocol deviations are determined and recorded whilst the study is ongoing, and the list is finalized prior to final database lock (and unblinding). All deviations are classified as either “critical” or “non-critical”. Only the critical (=major) protocol deviations will be presented in the tables. For more details, please refer to the Protocol Deviation Plan.

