#### **Table 14.2.1.1.1: ACR20: Summary with overall p-value and pairwise comparisons versus placebo**

Logistic regression model at each time point, modeling the responders. Factors in the model are: treatment, region, and previous use of biologics.

Per time point, the table will present:

- Overall type-III p-value for all explanatory factors in the model.
- Per group: number and percentage of responders, difference in percentage responders versus the placebo group (GLPG0634 minus placebo), together with a 95% confidence interval of this difference (as provided by SAS PROC FREQ).
- Per group: p-value for pairwise comparison versus the placebo group, derived from contrasts within the overall regression model. These p-values will be presented both as uncorrected p-values as well as corrected for multiplicity according to Hommel's closed-testing method (SAS PROC MULTTEST).

The "raw" SAS PROC output must be provided in a statistical appendix listing.

The table will show:

- NRI in ITT and in per-protocol
- LOCF in ITT and in per-protocol
- observed-case in ITT (descriptive at Week 12 + 24; inferential statistics at Week 12 only).

Table to be created for the Week 12 interim analysis as well, cut off at Week 12. ITT only.

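### As written, one per-protocol set spans all 24 weeks, so a deviation after Week 12 can remove a subject from the Week 12 per-protocol analysis

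*Protocol*

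**What the plan says.** Protocol 8.8.1.1 makes the PP analysis a confirmation of ITT: "A secondary per-protocol analysis will be performed to confirm the ITT analysis, excluding subjects with major protocol deviations". Its examples of major deviations are three baseline criteria (CRP, TJC68, SJC66) plus "<80% study medication compliance, or use of forbidden concomitant medications". It gives no time window and leaves full details to the SAP.

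SAP 2.1.1 defines PP once, in the efficacy row for periods 1 and 2 together, as ITT "excluding all critical (=major) protocol deviations. This is decided during the blind review meeting before final database lock". The row for the period after Week 12 has an ITT set only.

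SAP 7.2 adds: "Protocol deviations are determined and recorded whilst the study is ongoing". The list closes before final database lock, and further detail is referred to a Protocol Deviation Plan.

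SAP 8.1.2 presents Weeks 1 to 24. Table 14.2.1.1.1 shows the primary endpoint as "NRI in ITT and in per-protocol"; its interim version is ITT only. PP results are also planned for the other two ACR20 comparison tables (14.2.1.1.2-3), for DAS28(CRP) (14.2.1.4.1-6) and for EULAR response (14.2.1.4.15-17).

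SAP 7.8.1 derives compliance twice, up to the day before the Week 12 visit and over 24 weeks. Nothing says which figure decides PP membership.

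**The concern.** The primary endpoint is fixed at Week 12, but membership of the set used to confirm it is settled by 24 weeks of conduct. A subject who follows the protocol to Week 12 and takes a forbidden drug at Week 18 drops out of the Week 12 PP comparison if the text is followed.

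Such exclusion is made on events after the endpoint, and these may be a consequence of it: a subject who has not responded has more reason to seek other RA medication or stop taking capsules. It may also relate to arm. At Week 12, joint-count non-responders on placebo and 50 mg/day change treatment; for the rest, "Subjects in the other groups will maintain their randomized treatment until Week 24".

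For switchers the effect is odd in a further way. SAP 4.5.1 does not use their data after Week 12 in the 24-week efficacy analysis, yet a deviation on the new treatment could delete their valid Week 12 outcome.

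At stake is whether the PP result does its stated job. It could agree or disagree with ITT for reasons unrelated to what happened up to Week 12.

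**Working it through.** **1. The plan's own figures.** The documents give no figure for the PP set. The nearest are the power statements in Protocol 8.8.2 (85 per arm, alpha 0.05/6 per comparison, chi-square). With power = Φ{[|p2 − p1|√n − z√(2p̄(1 − p̄))] / √[p1(1 − p1) + p2(1 − p2)]}, where p̄ is the mean of p1 and p2 and alpha is two-sided:

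- 20% v 48%: 89.8% (stated 90%)
- 40% v 70%: 91.2% (stated 90%)
- 20% v 45%: 80.9% (stated 80%)
- 40% v 66%: 78.4% (stated 80%)

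These reproduce within 2 points. They serve only as a yardstick: the design differences are 25 to 30 points.

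**2. Which deviations can arise after Week 12.** Of the five examples in Protocol 8.8.1.1, the three baseline criteria cannot. Compliance and forbidden medication can.

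**3. Compliance.** Take 84 days to Week 12 (Day 85 − Day 1, as in SAP 7.8.1) and assume 84 more to Week 24. If the 24-week figure is the criterion:

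- 100% then 59%: (84 + 0.59 × 84)/168 = 79.5%. Removed from Week 12 PP despite a perfect first period.
- 65% then 100%: (0.65 × 84 + 84)/168 = 82.5%. Kept in Week 12 PP despite a poor first period.

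The set can therefore be wrong for Week 12 in both directions. A subject fully compliant to Week 12 has to fall below 60% afterwards to be removed, since (100 + 60)/2 = 80.

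**4. Effect on the Week 12 difference.** Let p be the Week 12 ACR20 rate, and dR and dN the proportions of responders and non-responders removed for later deviations. Then

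PP rate = p(1 − dR) / [p(1 − dR) + (1 − p)(1 − dN)].

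The documents give no deviation rates, so these are assumptions: p = 0.40 in both arms (no drug effect), dR = 0.03, dN from 0.05 to 0.20.

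- dN = 0.05: 0.388/(0.388 + 0.570) = 40.5%
- dN = 0.10: 0.388/(0.388 + 0.540) = 41.8%
- dN = 0.15: 0.388/(0.388 + 0.510) = 43.2%
- dN = 0.20: 0.388/(0.388 + 0.480) = 44.7%

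Spurious PP difference, active minus placebo:

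- equal dN in both arms: 0
- active 0.10, 0.15 or 0.20 against placebo 0.05: +1.3, +2.7 or +4.2 points
- the same rates reversed: −1.3, −2.7 or −4.2 points

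**5. With a true effect.** Take 20% v 48%, a difference of 28.0 points, with 5% of responders and 15% of non-responders removed. The PP difference is 28.9 points if both arms are affected (50.8% − 21.8%, from unrounded rates), 30.8 if only the active arm is (50.8% − 20.0%), and 26.2 if only placebo is (48.0% − 21.8%).

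**6. Subjects lost.** At p = 0.40, dR = 0.03, dN = 0.15: 0.40 × 0.03 + 0.60 × 0.15 = 10.2% of 85, about 9 per arm.

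**The case against.** The strongest reply is that the documents are silent on timing and do not lay down a 24-week rule. What counts as critical is left to the Protocol Deviation Plan and the blind review meeting, and that plan, which was not available, could contain a time rule. This stands as a limit. It does not remove the point, because the protocol promised the details in the SAP, and the SAP text, followed literally, excludes all critical deviations from a set applied at Week 12.

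Table 14.1.1.2 counts the analysis populations separately per study period, which might suggest a Week 12 PP set. But it is only a count, it refers to section 3.1 (relative days), and it fits the different sets per analysis chapter.

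A reader might infer that bias would favour the higher doses, because non-responders there stay on the same dose. The documents do not support a direction. Switching depends on joint counts, not ACR20, so a placebo ACR20 non-responder with enough joint improvement stays on placebo; switchers can also deviate on their new treatment, and treatment remains blinded.

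A reader might also see a contradiction with SAP 2.3.3, where for an unblinded subject "all efficacy data of this subject up to the point of unblinding will still qualify for the per-protocol efficacy analysis selection". That sentence goes on to require the same exclusion of critical deviations. It governs which data are usable after unblinding and does not date-limit deviations, so the contrast proves little.

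The objection on materiality stands: PP is secondary, no success rule depends on it, and only two of the five example deviations are involved.

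**Conclusion.** The point holds as a defect in how the Week 12 PP set is defined. As written, a deviation arising only in Weeks 13-24 can remove a subject from the analysis meant to confirm the Week 12 result. If 24-week compliance is the criterion, poor first-period compliance can also be masked.

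Size and direction cannot be found from the documents. Under the assumed rates the shift is at most about 4.2 points either way and may be zero, against design differences of 25 to 30 points. It would be wrong to infer that the primary conclusion is at risk: the primary analysis is ITT with non-responder imputation, the interim comparison is ITT only, and the type I error is untouched. The finding also rests on no time rule existing in the Protocol Deviation Plan. It is a minor improvement to a secondary analysis.

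**What to change.** In SAP 2.1.1, define two PP flags:

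- **Week 12 PP**, for all PP results up to and including Week 12: exclude critical deviations with onset on or before the Week 12 visit, and judge compliance on the first-period figure from SAP 7.8.1.
- **24-week PP**, for Weeks 16-24: exclude critical deviations over the full study, and judge compliance on the 24-week figure.

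Apply them in Tables 14.2.1.1.1-3, 14.2.1.4.1-6 and 14.2.1.4.15-17. Correct the section 3.1 cross-reference in Table 14.1.1.2. If the Protocol Deviation Plan already holds a time rule, state it in the SAP.

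The cost is SAP wording, an onset date for each critical deviation and one extra flag. Conduct, sample size and the primary analysis do not change.

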### 8.3.2 Inclusion Criteria

To be eligible for study entry subjects must fulfil all of the following criteria:

1. Male or female subjects who are  $\geq 18$  years of age, on the day of signing informed consent.
2. Diagnosis of RA since at least 6 months prior to Screening and meeting the 2010 ACR/EULAR criteria of RA and ACR functional class I-III.
3. Have  $\geq 6$  swollen joints (from a 66-joint count) and  $\geq 8$  tender joints (from a 68-joint count) at Screening and Baseline, and a Screening serum CRP  $\geq 0.7$  x upper limit of the normal (reference) laboratory range (ULN).
4. Have received MTX (oral or parenteral) for  $\geq 6$  months and have been on a stable dose (15 mg/week to 25 mg/week) of MTX for at least 4 weeks prior to Screening and willing to continue on this regimen for the duration of the study. Stable doses of MTX as low as 10 mg/week are allowed, when there is documented evidence of intolerance or safety issues at higher doses.
5. If taking oral steroids, these should be at a dose  $\leq 10$  mg/day of prednisone or prednisone equivalent and stable for at least 4 weeks prior to Baseline.
6. If taking non-steroidal anti-inflammatory drugs (NSAIDs), these must be at a stable dose for at least 2 weeks prior to Baseline.
7. The results of the following laboratory tests performed at the central laboratory at Screening must be within the limits specified below:

CONFIDENTIAL

- a) Hemoglobin  $\geq 10$  g/dL (International System of Units [SI]:  $\geq 100$  g/L);
  - b) WBCs  $\geq 3.0 \times 10^3$  cells/mm^3 (SI:  $\geq 3.0 \times 10^9$  cells/L);
  - c) Neutrophils  $\geq 2.0 \times 10^3$  cells/mm^3 (SI:  $\geq 2.0 \times 10^9$  cells/L);
  - d) Lymphocytes  $\geq 1.0 \times 10^3$  cells/mm^3 (SI:  $\geq 1.0 \times 10^9$  cells/L);
  - e) Platelets  $\geq 100 \times 10^3$  cells/mm^3 (SI:  $\geq 100 \times 10^9$  cells/L);
  - f) Serum ALT and aspartate aminotransferase (AST)  $\leq 1.5 \times$  ULN;
  - g) Total bilirubin level  $\leq 1.25 \times$  ULN;
  - h) Alkaline phosphatase  $\leq 1.5$ ULN;
  - i) Lipase  $\leq 1.5 \times$  ULN and amylase  $\leq 1.5$ ULN;
  - j) Creatinine clearance  $>60$  mL/min. Creatinine clearance will be calculated using the Cockcroft-Gault formula.

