### **8.8. ACR COMPONENT: SERUM CRP**

#### **8.8.1. Parameters**

Serum CRP (mg/L) will be analyzed as raw values, change from baseline and percent change from baseline.

Note that if for a specific visit both the regular CRP as well as the high-sensitive CRP are available, the high-sensitive CRP will be used in the analysis tables and figures. The regular CRP will then only be listed.

CRP and hsCRP values will also be categorized according to the lab’s normal ranges: normal (value  $\leq$  ULN) or high (value  $>$  ULN), where ULN = upper limit of the normal range as provided by the central lab. Note that the same ULN (8.999) will be applied to both CRP and hsCRP.

Note that CRP and hsCRP will be excluded from the lab safety analysis.

Note that the percentage change from baseline remains missing if the baseline value itself equals zero.

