### **Table 14.2.1.8.1: Serum CRP (mg/L): Descriptive statistics of the actual values**

### **Table 14.2.1.8.2: Serum CRP (mg/L): Descriptive statistics of the change from baseline**

### **Table 14.2.1.8.3: Serum CRP (mg/L): Descriptive statistics of the percent change from baseline**

(descriptive statistics at all time points; frequency table at weeks 12 + 24)

Overall as well as split up for subjects with a baseline CRP > ULN versus  $\leq$  ULN.

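### The per-protocol set counts a normal-range Baseline CRP as a major deviation, although eligibility sets a CRP limit only at Screening and only at 0.7 x ULN

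*Protocol*

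**What the plan says.** Protocol section 8.8.1.1 states that "A secondary per-protocol analysis will be performed to confirm the ITT analysis", and names examples of what removes a subject: "excluding subjects with major protocol deviations (such as Baseline CRP within normal range, Baseline TJC68 <8, Baseline SJC66 <6", followed by low compliance and forbidden concomitant medication. It leaves the full list to the SAP.

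Inclusion criterion 3 (Protocol section 8.3.2, repeated in the synopsis) sets joint-count limits at both visits but ties CRP to one visit: "tender joints (from a 68-joint count) at Screening and Baseline, and a Screening serum CRP" of at least 0.7 x ULN. No inclusion or exclusion criterion mentions Baseline CRP. Footnote 5 of the flow chart (section 8.7.1.5) describes the Baseline check as "Eligibility criteria check based on the laboratory results from the Screening visit".

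SAP section 2.1.1 defines the per-protocol set as a "subpopulation of ITT, excluding all critical (=major) protocol deviations", to be settled at the blind review meeting. SAP section 7.2 refers to a separate Protocol Deviation Plan for details. Neither section repeats or withdraws the CRP item. On the limit itself, SAP section 8.8.1 says: "Note that the same ULN (8.999) will be applied to both CRP and hsCRP".

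**The concern.** A per-protocol set should drop subjects who departed from the protocol in a way that matters for efficacy. Here one criterion drops subjects who complied. It differs from the entry rule in both visit (Baseline instead of Screening) and threshold (1.0 instead of 0.7 x ULN).

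The per-protocol set is used for the ACR20 tables, including the primary time point (Tables 14.2.1.1.1 to 14.2.1.1.3), for the main DAS28(CRP) tables (14.2.1.4.1 to 14.2.1.4.6) and for EULAR response (14.2.1.4.15 to 14.2.1.4.17). CRP is one of the ACR core items and a term in DAS28(CRP), so the rule also selects on the baseline level of an outcome component.

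If ITT and per-protocol results differ, the reader cannot tell whether the cause is adherence or the shift to higher-CRP patients. If they agree, the agreement concerns a narrower population than the one enrolled.

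**Working it through.** **Step 1. Compare the deviation items with the entry rule.**

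| Item | Entry rule (Protocol 8.3.2, criterion 3) | Major deviation (Protocol 8.8.1.1) | Match |
|---|---|---|---|
| TJC68 | at least 8 at Screening and Baseline | below 8 at Baseline | yes |
| SJC66 | at least 6 at Screening and Baseline | below 6 at Baseline | yes |
| CRP | at least 0.7 x ULN at Screening | within normal range at Baseline | no: visit and threshold both differ |

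**Step 2. Put the limit in mg/L.** With ULN = 8.999 (SAP 8.8.1), the entry limit is 0.7 x 8.999 = 6.30 mg/L. SAP 8.8.1 classes a value at or below ULN as normal. Two kinds of fully eligible subject therefore become major deviators:

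- CRP from 6.30 to 8.999 mg/L at both visits;
- CRP above 8.999 mg/L at Screening and at or below it at Baseline.

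**Step 3. Look for a correction elsewhere.** SAP 6.3.1 reports no change to the protocol-specified analyses before the interim lock, and the later changes in SAP 6.3.2 do not touch this item. I found no passage that reconciles the two rules.

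**Step 4. Reproduce the protocol's power.** Inputs from Protocol 8.8.2: n = 85 per arm, alpha = 0.05/6 = 0.0083 (sidedness not stated; taken as two-sided), chi-square test. With p̄ = (p1 + p2)/2,

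power = Φ{ [ |p2 − p1|·√n − z·√(2·p̄·(1 − p̄)) ] / √( p1(1 − p1) + p2(1 − p2) ) }, z = 2.638.

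For 20% versus 48%: (0.28 x 9.220 − 2.638 x 0.670) / 0.640 = 1.27, so power is 0.898. The other three stated pairs give 0.912 (40% vs 70%), 0.809 (20% vs 45%) and 0.784 (40% vs 66%), against stated values of 90%, 80% and 80%. The protocol's figures are reproduced to within two percentage points.

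**Step 5. Power if the CRP item alone removes a given share of each arm.**

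| Share removed | n per arm | 20% vs 48% | 40% vs 70% |
|---|---|---|---|
| 0% | 85 | 0.898 | 0.912 |
| 10% | 76.5 | 0.857 | 0.874 |
| 15% | 72.25 | 0.831 | 0.849 |
| 20% | 68 | 0.801 | 0.821 |
| 30% | 59.5 | 0.730 | 0.753 |
| 35% | 55.25 | 0.688 | 0.711 |

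**Step 6. What share is plausible?** The documents do not say, so this step is an assumption throughout. CRP was simulated as log-normal, with median 8 to 16 mg/L before selection, between-subject log-SD 0.9 to 1.1 and within-subject log-SD 0.3 to 0.6 (2 million subjects per scenario). Subjects with Screening CRP of at least 6.30 mg/L were kept. Of these, 14.3% to 34.6% had Baseline CRP at or below 8.999 mg/L. Subjects above ULN at Screening who fell to normal by Baseline made up about 7% to 22% of those eligible. The lowest total came with median 16, between-subject SD 1.1 and within-subject SD 0.3; the highest with median 8, 0.9 and 0.6. That leaves about 55 to 73 of 85 per arm before any true deviation is counted.

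**The case against.** The mismatch in wording is not disputed; the case on the other side concerns what follows from it.

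- **The list is illustrative.** The CRP item is given as an example, the SAP leaves the set to blind review, and the Protocol Deviation Plan is not available here. This stands in part: the text does not show that anyone was or will be removed. It does direct the blind review to treat the item as major, and nothing in the protocol or SAP withdraws it.
- **The per-protocol set is secondary.** The primary endpoint is ACR20 at Week 12 in ITT with non-responder imputation. SAP 6.1.2.1 names observed-case and LOCF as its confirmatory analyses, the interim ACR20 and DAS28 tables are ITT only, and no decision rule uses a per-protocol result. Baseline CRP is measured before dosing, so the exclusion should not by itself bias between arms. All of this stands and limits the weight of the point. Protocol 8.8.1.1 nevertheless gives the per-protocol analysis a confirming role, and that role is what the rule damages.
- **The size is assumed.** Correct. The 14 to 35% depends on chosen inputs, and the protocol never claims power for the per-protocol set. The power figures use the Bonferroni level, whereas the planned Hommel procedure is at least as powerful, so absolute power may be somewhat understated.
- **The SAP's CRP categories prove little.** The SAP tabulates CRP percent change "Overall as well as split up for subjects with a baseline CRP > ULN versus" at or below ULN, and SAP 7.5.1 has a class for 0.7 to 1.0 x ULN. These show that such subjects are anticipated. They are not proof that the SAP regards them as compliant, because ITT tables include deviators and the same list has a class below 0.7 x ULN. The conclusion does not need this support.

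**Conclusion.** The concern holds. As written, Protocol 8.8.1.1 classes as major deviators subjects who met every CRP entry rule. This follows from comparing sections 8.8.1.1 and 8.3.2 and needs no distributional assumption.

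The harm is to the interpretation and precision of the per-protocol ACR20, DAS28(CRP) and EULAR analyses. The primary result and the planned sample size are not affected. The number of subjects lost cannot be known from the documents. Under the assumed CRP distributions it is 14 to 35% of those eligible, with per-comparison power for 48% versus 20% falling from 90% to about 83% at a 15% loss and 69% at a 35% loss. The item should be corrected, but it does not threaten the trial's main conclusion.

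**What to change.** In Protocol 8.8.1.1 and in the list of critical deviations, replace the Baseline CRP item with Screening CRP below 0.7 x ULN, so that CRP removes only subjects who violated criterion 3. If the Protocol Deviation Plan already uses the entry criterion, align the protocol text with it. State the major deviations in SAP 2.1.1 or 7.2, since the protocol leaves them to the SAP. If the protocol is not amended, record the change in SAP 6.3, which is kept for departures not covered by an amendment.

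If patients with raised CRP are of interest, report Baseline CRP above ULN as a labelled subgroup. Tables 14.2.1.1.10 (ACR20) and 14.2.1.4.7 (DAS28 change) already tabulate results by baseline CRP class.

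The cost is one definition and the matching deviation entry, settled before the blind review meeting and final database lock. No new data are needed, no subject is affected, and no stated sample size or power figure changes.
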